EuroQol 5-Dimension 5-Level (EQ-5D-5L): EQ-5D-5L questionnaire is a widely used, generic questionnaire that assesses health status (The EuroQol Group 1990; Herdman et al. 2011). This is a patient-rated scale. The questionnaire consists of 2 parts. The first part assesses 5 dimensions (mobility, self-care, usual activities, pain/discomfort, and anxiety/depression) that have 5 possible levels of response (no problems, slight problems, moderate problems, severe problems, extreme problems). This part of the EQ-5D can be used to generate a health state index score, which is used to compute quality-adjusted life years for utilization in health economic analyses. The health state index score is calculated based on the responses to the 5 dimensions, providing a single value on a scale from less than 0 (where 0 is a health state

equivalent to death; negative values are valued as worse than death) to 1 (perfect health), with higher scores indicating better health utility. The second part of the questionnaire consists of a visual analog scale on which the patient rates their perceived health state from 0 (the worst health you can imagine) to 100 (the best health you can imagine). The EQ-5D-5L will be captured at Visit 2 and at 0 and 24 hours postdose of study drug.

Disability: Disability will be measured by determining the level of interference with normal activities with 4 response options including not at all; mild interference, marked interference; and need complete bed rest. This will be evaluated at 0 (pre dose), 0.5, 1, 2, and 24 hours postdose of study drug.

PGI-C: Patient global impression of change will be measured at 2 and 24 hours postdose of study drug with a 7-point scale ranging from very much better to very much worse.

Treatment Satisfaction: Treatment satisfaction will be evaluated at 48 hours postdose of the study drug by determining the patient's level of satisfaction (ranging from extremely dissatisfied to extremely satisfied); their willingness to take this treatment again (ranging from strongly disagree to strongly agree); if they would they recommend this treatment to another patient (ranging from strongly disagree to strongly agree) and their preference when comparing this treatment to the previous treatment ("prefer this treatment in comparison to my previous treatment" to "prefer my previous treatment in comparison to this treatment").

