- Sec. 5.6.3 (Details of Efficacy Analyses): In [Table LAIH. 5.3](#), ANCOVA was changed to ANOVA because ANOVA was the actual method for analyses.
- Sec. 5.6.3 (Details of Efficacy Analyses): Figures for ratio of achieving Pain Free, Pain Relief, and MBS-free, MBS-Free by Chosen Symptom up to 2 hours were added.
- Sec. 5.7.1 (Adverse Events): “AEs” were explicitly defined as “AEs are collected from Visit 1 to Visit 3.”
- Sec. 5.7.1 (Adverse Events): “Post-dose AEs” were defined as the same as the TEAE except without the restriction of the 48 hours cutoff after the dosing. In addition, its TFLs would be created.
- Sec. 5.7.1 (Adverse Events): “By PT by decreasing frequency with an incidence in any lasmiditan group $\geq 1.5\%$ and greater than placebo” was changed to “By PT by decreasing frequency with an incidence in any lasmiditan group $\geq 1.5\%$ and PT including “Vertigo.””
CCI
[REDACTED]
- Sec. 5.7.1 (Adverse Events): (AE): From “overview of AEs”, total number of events is deleted because it would not be used in CSR. “Pot-dose AEs” is added.
- Sec. 5.7.3 (Vital Signs and Weights): The wording “treatment emergent” was deleted because by nature, Vital Signs and weights were measured at Visit 3 which were beyond 48 hours from dosing, in general.
- Sec. 5.7.3 (Vital Signs and Weights): BMI was added.
- Sec. 5.7.4 (Laboratory Tests): The wording “treatment emergent” was deleted because by nature, lab tests were taken at Visit 3 which were beyond 48 hours from dosing, in general.
- Sec. 5.7.4 (Laboratory Tests): Both standard and conventional units’ outputs for continuous analysis were specified.
- Sec. 5.7.7 (Safety Topics of Interest): This section was newly added. **CCI**
[REDACTED]
- Sec. 5.8 (Subgroup Analysis): The analysis “Patients who fail the most recent triptan at any time before screening” was renamed as “Triptan responder vs. insufficient responder (based on the most recent triptan experience)” to clarify the definition (subgroup ID= SUB1).
- Sec. 5.8 (Subgroup Analysis): “Patients with one or more CVRF” was updated as “Patients with two or more CVRF” (subgroup ID= SUB12).
- Sec. 5.8 (Subgroup Analysis): New subgroup definitions and analyses were added. The entire subgroup analysis was summarized in [Table LAIH. 5.6](#).

- Sec. 5.8 (Subgroup Analysis): Analysis methods and statistical models were specified.

4. Study Objectives

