
 • To evaluate the efficacy of lasmiditan 200 mg, 100 mg, and 50 mg on freedom from MBS compared to placebo • To evaluate the efficacy of lasmiditan 200 mg and 50 mg on pain relief compared to placebo • To evaluate the efficacy of lasmiditan 200 mg, 100 mg, and 50 mg on sustained freedom from pain compared to placebo • To evaluate the efficacy of lasmiditan 200 mg, 100 mg, and 50 mg at 2 hours on freedom from symptoms associated with migraine compared to placebo • To explore the time course of lasmiditan 200 mg, 100 mg, and 50 mg efficacy compared to placebo • To evaluate the efficacy of lasmiditan 200 mg, 100 mg, and 50 mg on disability during migraine attacks compared to placebo • To evaluate the efficacy of lasmiditan 200 mg, 100 mg, and 50 mg on health utility compared to placebo • To evaluate the efficacy of lasmiditan 200 mg, 50 mg, and 100 mg on Patient Global Impression of Change (PGI-C) compared to placebo • To evaluate the efficacy of lasmiditan 200 mg, 100 mg, and 50 mg on Health-Related Quality of Life (HRQoL) during an acute migraine attack compared to placebo 	
 • The proportion of patients in each group who are free of MBS associated with migraine at 2 hours postdose during the attack • The proportion of patients with pain relief in each group at 2 hours postdose during the attack • The proportion of patients in each group with 24-hour and 48-hour sustained pain freedom during the attack defined as pain free at 2 and 24 hours, and 2 and 48 hours, respectively, with no rescue medication • The proportion of patients in each group that are free of symptoms associated with migraine at 2 hours postdose during the attack, including each of the following: phonophobia, photophobia, nausea, and vomiting • The proportion of patients in each group at each time point with pain freedom, pain relief, freedom from MBS, and no disability after taking the dose of study drug during the attack • The proportion of patients in each group with no disability as measured by the disability item, at 2 hours postdose during the attack • Mean change from baseline in utility in each group as measured by the EuroQol 5 dimension 5-level scale (EQ-5D-5L), at 24 hours postdose during the attack • The proportion of patients in each group very much or much better as measured by PGI-C, at 2 and 24 hours postdose during the attack • Mean HRQoL score for domains of social functioning, migraine symptoms, and feelings/concerns, as measured by the 24-hour Migraine Quality of Life Questionnaire (MQoLQ), in each group at 24 hours postdose of study during the attack

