5.4. General Statistical Considerations

Statistical analysis of this study will be the responsibility of Lilly or its designee.

In general, we will use the following statistical methods unless otherwise specified. For detailed definitions of [T1] (primary objectives), [T2] and [T3] (2 key secondary objectives), see Section [5.6.1](#):

- For efficacy analyses based on proportion, the logistic regression used in [T1] will be applied. The model term includes treatment and baseline usage of preventive medications to reduce the frequency of migraine (Yes/No).
- When treatment group (PLA, LY50, LY100, LY200) is in a statistical model, it will be regarded as a categorical variable.
- For analysis based on continuous variable (change from baseline), if analysis of variance (ANOVA) is used then its covariate includes treatment and baseline usage of preventive medications to reduce the frequency of migraine (Yes/No). LSMeans will be used for estimation.
- For safety analyses and demographics, only descriptive statistics will be presented, and no statistical test will be conducted.
- Statistical tests will be conducted at a 2-sided significance level of 0.05. The 95% confidence interval will be presented if appropriate.
- No multiplicity adjustment for multiple tests (between the arms for the same efficacy objective, nor between the different objectives for the same arms) will be made except primary and two key secondary analyses ([T1], [T2], and [T3]).
- Analyses will be reported by 4 treatment groups (PLA, LY50, LY100, LY200) in general.
- Frequency tables such as those for AE or TEAEs will be sorted by LY_ALL, in decreasing frequency.
- For safety, 5 treatment groups (PLA, LY50, LY100, LY200, LY_ALL) will be displayed.
- For demographics, 6 treatment groups (PLA, LY50, LY100, LY200, LY_ALL, Overall) will be displayed. Here “Overall” means all combined arms (PLA + LY_ALL).
- For efficacy analyses based on proportions, odds ratio along with 95 % confidence interval will be calculated at 2 hours post-dose time point (each treatment vs. placebo).

- When Cochran-Mantel-Haenszel test is used for a multi-category response, baseline usage of preventive medications to reduce the frequency of migraine (Yes/No) is used for stratification (each treatment vs. placebo).

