5.6.3. Details of Efficacy Analyses

Table LAIH. 5.3 is the list of primary/ key secondary/ other secondary/ exploratory analysis with each analysis population, timeframe and analysis method.

Table LAIH. 5.3 Primary, Key Secondary, Other Secondary and Exploratory Efficacy Variables and Analysis Methods

ID	Type	efficacy variables	POP	Timeframe	Analysis
1	PRIM /2 ND	Headache Pain Free	mITT/ ITT/ PPS	up to 48h	LOGISTIC
2	2KEY	Pain Free Trend Test	mITT/ ITT/ PPS	2h	CA
3	2KEY /2ND	Headache Pain Relief	mITT/ ITT/ PPS	up to 48h	LOGISTIC
4	2 ND	MBS-Free	mITT/ ITT/ PPS	up to 48h	LOGISTIC
5	2 ND	Migraine Symptoms Present at Assessment Times (Nausea, Phonophobia, Photophobia, Vomiting)	ITT	up to 48h	LOGISTIC
6	OTH	MBS-Free by Chosen Symptom: (Nausea, Phonophobia, Photophobia)	ITT	up to 48h	LOGISTIC
7	2 ND	Time to Headache Pain Free Through 48 Hours Post-Dose	ITT	up to 48h	KM
8	2 ND	Time to Headache Pain Relief Through 48 Hours Post-Dose	ITT	up to 48h	KM
9	2 ND	Time to MBS-Free Through 48 Hours Post-Dose	ITT	up to 48h	KM
10	OTH	Time to MBS-Free by Chosen Symptom Through 48 Hours Post-Dose: (Nausea, Phonophobia, Photophobia)	ITT	up to 48h	KM
11	2 ND	Disability	ITT	0.5h/1h/2h/24h	LOGISTIC

12	OTH	Incidence of Rescue or Recurrence Medication Use	ITT	[0h-2h]/ [2h-24h]/ [24h-48h]	LOGISTIC
13	OTH	Incidence of Headache Recurrence Through 24/48 Hours Post-Dose	ITT	2h< recurrence <=24h 2h< recurrence <=48h	LOGISTIC
14	2 ND	PGI-C	ITT	2h/24h	LOGISTIC
15	2 ND	Sustained Pain Free at 24 Hours and 48 Hours	ITT	24h/48h	LOGISTIC
16	2 ND	Time to No Disability Through 24 Hours	ITT	up to 24h	KM
17	OTH	Summary of Symptom-Free at Assessment Times (Nausea, Phonophobia, Photophobia, Vomiting)	ITT	up to 48h	LOGISTIC
18	OTH	Total Migraine Freedom	ITT	up to 48h	LOGISTIC
19	OTH	Modified Sustained Pain Free at 24 Hours and 48 Hours	ITT	24h/48h	LOGISTIC
20	OTH	Time to Meaningful Pain Relief Through 48 Hours	ITT	up to 48h (including 6h/8h)	KM
21	OTH	Time to Pain Free Through 48 Hours	ITT	up to 48h (including 6h/8h)	KM
22	2 ND	Change from Baseline of EQ-5D-5L in Index Score	ITT	24h	ANOVA
23	2 ND	Change From Baseline of EQ-5D-5L in Visual Analog Scale	ITT	24h	ANOVA
24	2 ND	HRQoL Measured by MQoLQ in 5 Domains	ITT	24h	ANOVA
25	2 ND	Treatment Satisfaction	ITT	48h	CMH

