If patients are pain free and are not experiencing any other migraine symptoms (i.e. nausea, photophobia, phonophobia, or vomiting), then they are total migraine free.

Modified Sustained Pain Free at 24 hours and 48 hours

Modified Sustained Pain-Free is defined as experiencing headache pain-free at two hours after the dose and no moderate or severe pain at the indicated assessment time, having not used any medications to treat migraine after the dose up to the assessment timing. Note that if a patient has missing evaluation at 24 hours, then he is excluded from the analysis instead of setting his response as nonresponder. The same is true at 48 hours evaluation.

Time to Meaningful Pain Relief Through 48 Hours

Meaningful Pain Relief timing is defined as the time when the corresponding eDiary question is answered as Yes.

Time to Pain Free Through 48 Hours

Pain Free timing is defined as the time when the corresponding eDiary question is answered as Yes.

Change from Baseline of EQ-5D-5L in Index Score

It is based on the EQ-5D Health Status Index Score. The Japan specific tariffs (Japanese population-based index value) for the EQ-5D Health Status Index Score is used. Change from baseline is based on Baseline (0 hour) and post-baseline (24 hours).

Change from Baseline of EQ-5D-5L in Visual Analog Scale

The change of EQ-5D-5L visual analog scale is based on Baseline (0 hour) and post-baseline (24 hours) from the onset of dosing.

HRQoL Measured by MQoLQ in 5 Domains

There are 5 domains in MQoLQ. Each domain will be analyzed separately: work functioning, social functioning, energy and vitality, feelings and concerns, and migraine symptoms. Each domain consists of 3 questions answered on a 7-point scale where 1 indicates maximum impairment and 7 indicating no impairment. A domain score is calculated by summing the responses to the 3 questions and the domain score ranges from 3 to 21. The response variable in this analysis is raw values at 24 hours.

Treatment Satisfaction

There are 4 questions. Each question will be analyzed separately. Distribution of responses and proportion of patients with agree or strongly agree will be summarized for each treatment group:

- the patient's level of satisfaction (ranging from extremely dissatisfied to extremely satisfied)
- their willingness to take this treatment again (ranging from strongly disagree to strongly agree)

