5.8. Subgroup Analysis

Subgroup analysis is summarized in [Table LAIH. 5.6](#).

- For efficacy analyses based on proportion, the logistic regression used in [T1] will be applied to each subgroup separately. The model term includes treatment and baseline usage of preventive medications to reduce the frequency of migraine (Yes/No). The odds ratio (relative to placebo), its 95% confidence interval, and p-value will be calculated based on this model.
- For efficacy analyses based on proportion, additional logistic regression will be used. The model term includes treatment, baseline usage of preventive medications to reduce the frequency of migraine (Yes/No), subgroup, and treatment-by-subgroup interaction. The p-value for treatment-by-subgroup interaction will be displayed. The level of significance for interaction (2-sided test) is defined as 0.05 (See Section [5.4](#)).
- For efficacy analyses based on continuous variables, ANOVA will be used for each subgroup separately. The model includes treatment and baseline usage of preventive medications to reduce the frequency of migraine (Yes/No). Change from baseline and p-values for treatment comparison will be calculated.
- For efficacy analyses based on continuous variables, additional ANOVA will be used for The model includes treatment, baseline usage of preventive medications to reduce the frequency of migraine (Yes/No), subgroup, and treatment-by-subgroup interaction. The p-value for treatment-by-subgroup interaction will be displayed. The level of significance for interaction (2-sided test) is defined as 0.05.

Table LAIH. 5.6 Subgroup Analysis

ID	Type	Analysis population [Note 1]	Dmg	PF/PR/ MBS/ Disa. at 2h	PGI-C at 2h/24h, Satisf. at 48 h	TEAE by PT	Other Analysis
SUB1	Triptan responder vs. insufficient responder (based on the most recent triptan experience)	mITT and patients who has triptan experience in lifetime	O		O	O	[1] PF/PR/MBS/disability time course (up to 48 hours) [2] EQ-5D-5L at 24h [3] Triptan detail summary at baseline

ID	Type	Analysis population [Note 1]	Dmg	PF/PR/ MBS/ Disa. at 2h	PGI-C at 2h/24h, Satisf. at 48 h	TEAE by PT	Other Analysis

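### The two EQ-5D-5L change endpoints are analysed without the hour-0 score as a covariate, which can cost precision and saves nothing

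*SAP*

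**What the plan says.** The health-utility endpoint in SAP Table LAIH. 4.1 is "Mean change from baseline in utility in each group as measured by the EuroQol 5 dimension 5-level scale (EQ-5D-5L), at 24 hours postdose". SAP Table LAIH. 5.3 lists it as ID 22 and adds the visual analogue scale as ID 23. Both are labelled other secondary, use the ITT population at 24 hours, and are assigned to ANOVA. SAP 5.6.3 takes hour 0 as the baseline for both. Protocol 9.1.2 confirms that the data exist: "The EQ-5D-5L will be captured at Visit 2 and at 0 and 24 hours postdose of study drug".

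The model is in SAP 5.4: "if analysis of variance (ANOVA) is used then its covariate includes treatment and baseline usage of preventive medications" (yes or no), with estimation by LSMeans. No section adds the hour-0 score. The revision history in SAP Section 3 shows that this is deliberate: for Table LAIH. 5.3, "ANCOVA was changed to ANOVA because ANOVA was the actual method for analyses". SAP 5.8 carries the model into the subgroups, "For efficacy analyses based on continuous variables, ANOVA will be used for each subgroup separately", with the same two terms. EQ-5D-5L at 24 hours is analysed in SUB1, SUB18 and SUB20.

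**The concern.** A change score uses the baseline value by subtracting it in full. That is the best use of it only if patients one point apart at hour 0 are expected to be one point apart at 24 hours. There is reason to doubt that here. Hour 0 falls within a moderate or severe attack, and both scales have a ceiling (1 for the index, 100 for the visual analogue scale), so patients who start lower have more room to improve. That suggests a slope below 1. It is reasoning from the design, because the documents report no EQ-5D-5L data.

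If the slope is not 1, two things follow. The treatment difference has a larger variance than it needs to have. A fraction (1 - slope) of any chance hour-0 difference between arms also stays in the estimate. What can be lost is confidence-interval width and power for the health-utility objective. The effect is greater in the subgroups, where arms are smaller and chance imbalance is larger.

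**Working it through.** **Inputs from the documents.** Planned arm sizes are 190, 81, 190 and 163 for placebo, 50, 100 and 200 mg (SAP 5.2). Tests are two-sided at 0.05 (SAP 5.4). The plan states no power for EQ-5D-5L. Its only power figures are for [T1] to [T3] (93.6%, 94.9%, 91.2%, jointly 85.6%). These recompute to 95.0%, 94.9%, 92.2% and 86.8%, and have no bearing on this point.

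**Assumed inputs.** Let rho be the correlation between the hour-0 and 24-hour scores, and k = SD(24 h)/SD(0 h). I use rho of 0.2, 0.5 and 0.7, k from 0.75 to 2, and for power a treatment effect of 0.25 hour-0 SD.

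**Formulas**, in units of the hour-0 variance:

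- Planned change score: V_plan = 1 + k² - 2·rho·k
- Adjusted for hour 0, common slope: V_adj = k²(1 - rho²)
- Difference: V_plan - V_adj = (1 - rho·k)², never negative, and zero only when the slope rho·k equals 1
- Extra patients needed by the plan: (1 - rho·k)² / [k²(1 - rho²)]

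Worked case, k = 1 and rho = 0.5: V_plan = 1 + 1 - 1 = 1.00; V_adj = 1 - 0.25 = 0.75; excess = 0.25/0.75 = 33%; standard error larger by √1.333 - 1 = 15%.

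**Extra patients needed by the planned analysis**

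| k | rho 0.2 | rho 0.5 | rho 0.7 |
|---|---|---|---|
| 0.75 | 134% | 93% | 79% |
| 1 | 67% | 33% | 18% |
| 1.5 | 23% | 4% | 0.2% |
| 2 | 9% | 0% | 8% |

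**Power, 200 mg against placebo.** Power = Φ(0.25/SE - 1.96), with SE = √[V(1/190 + 1/163)] = 0.1068·√V. For k = 1 and rho = 0.5, the plan gives 0.25/0.1068 - 1.96 = 0.38, or 65%. With adjustment, 0.25/0.0925 - 1.96 = 0.74, or 77%.

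| k | rho 0.2 (plan / adjusted) | rho 0.5 | rho 0.7 |
|---|---|---|---|
| 1 | 46% / 67% | 65% / 77% | 86% / 91% |
| 1.5 | 30% / 36% | 42% / 44% | 59% / 59% |

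At k = 0.75 and rho 0.2 the figures are 55% and 89%. At k = 2 and rho 0.5 both are 27%.

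**Chance imbalance at hour 0**, 95% range: 1.96·√(1/190 + 1/163) = ±0.21 SD for 200 mg against placebo, and 1.96·√(1/190 + 1/81) = ±0.26 SD for 50 mg against placebo. With a slope of 0.5, half of this (0.10 and 0.13 SD) stays in the planned estimate.

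**Simulation** of the four-arm model with the preventive-use term, k = 1, 6,000 trials: the ratio of adjusted to planned variance was 0.61, 0.75 and 0.85 at rho 0.2, 0.5 and 0.7, against (1 + rho)/2 = 0.60, 0.75 and 0.85. Type I error was 0.046 to 0.056 across the two models.

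**The case against.** ANOVA on change, adjusted for the stratification factor, is a valid pre-specified analysis. Version 2 of the SAP confirms it, and Protocol 10.3.3.1 leaves the methods for these endpoints to the SAP. They lie outside the gatekeeping, and no power is claimed for them. All of this stands, and it limits the weight of the point.

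The size is assumed throughout and the table contains cells with no loss, so a material loss in this trial is not shown. That stands too. It does not favour the plan, however: with the covariate the slope is estimated from the data, so rho and k need not be known.

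The guarantee of no loss needs a slope common to the arms. With unequal slopes and 7:3:7:6 allocation, a common-slope ANCOVA can do slightly worse for one contrast. With simulated slopes of 0.6, 1.0, 0.7 and 0.7 (placebo to 200 mg), its variance for 50 mg against placebo was about 4% larger; in a more extreme case one contrast lost about 7%. The other contrasts gained in both. With slopes of 0.4, 0.7, 0.5 and 0.5 every contrast gained.

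Three qualifications of scope also stand. Missing EQ-5D-5L values are not imputed (SAP 5.4.1), so the analysed patients may be fewer than the planned sizes; this changes the absolute power and the imbalance ranges but not the variance ratios. The subgroup analyses use mITT, and the visual analogue scale is not part of the health-utility objective in Table LAIH. 4.1. Finally, SAP version 2 dropped the condition that the eDiary baseline precede dosing, so some hour-0 scores may be post-dose. That affects the change score as much as the covariate.

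**Conclusion.** The concern holds as an optional improvement in efficiency, not as an error. The hour-0 score that each change score already requires is left out of the model for IDs 22 and 23 and their subgroup analyses. Given a common slope, the planned analysis is never more precise than the adjusted one, and it matches it only when the slope is 1. With equal standard deviations, it needs 18% to 67% more patients for correlations from 0.7 down to 0.2; over all the assumptions examined the range is 0% to 134%. The estimate is unbiased under randomisation, type I error is preserved, and [T1] to [T3] are unaffected. The point does not extend to the MQoLQ domains (ID 24), which are analysed as raw 24-hour values.

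**What to change.** In SAP 5.4 and Table LAIH. 5.3, specify ANCOVA on the change score for IDs 22 and 23. The terms are treatment, preventive use (yes/no) and the hour-0 value of the same measure as a continuous covariate: the index for ID 22, the visual analogue scale for ID 23. Report LSMeans as now planned. Add the same term to the EQ-5D-5L models in SAP 5.8. Keep the planned ANOVA as a sensitivity analysis. If any hour-0 entries were made after dosing, a further sensitivity analysis without those patients would be sensible.

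The cost is one model term (one degree of freedom out of about 600) and SAP wording before database lock. No new data are needed and the endpoint and population stay the same. No patient is lost, because a patient without an hour-0 score has no change score to analyse. The protocol leaves these methods to the SAP, so it needs no amendment.
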